5 STUDY ENROLLMENT AND WITHDRAWAL

5.1 PARTICIPANT INCLUSION CRITERIA

1. Age \geq 75 years
2. LVEF \leq 35% by cardiac imaging including echocardiogram, nuclear imaging, cardiac catheterization, or cardiac magnetic resonance imaging
3. QRS width $>$ 120 ms on surface electrocardiogram
4. New York Heart Association class II, III, or ambulatory IV for HF
5. Patient undergoing de novo CRT device implantation or CRT-D device change-out for battery depletion

5.2 PARTICIPANT EXCLUSION CRITERIA

1. Patient within 40 days of acute myocardial infarction
2. Patient within 3 months of cardiac revascularization (percutaneous coronary intervention or bypass surgery)
3. Patient with prior history of cardiac arrest or documented sustained ventricular arrhythmia
4. Patient with expected longevity $<$ 1 year
5. Patient not on optimal medical therapy for HF management including when tolerated β -blockers, angiotensin converting enzyme inhibitors or angiotensin receptor blockers
6. Patient unable or unwilling to sign a written informed consent
7. Patient's with dementia that are unable to consent for themselves
8. Participating in any other clinical trials (observational/registries allowed)

5.3 OBSERVATIONAL SUBJECT ENROLLMENT

Patients identified in Aim 1 who refuse to participate will be offered to enroll in the observational cohort of Aim 2. Patients are eligible to enroll in the observational cohort at the time of implant through fourteen days' post procedure. There is a separate written, informed consent designed specifically for the prospective observational study. Sites are to collect, from all patients enrolled in Aim 2, their reason(s) why they refused enrollment in Aim 1. It is anticipated that a majority of these patients will accept participating in the observational study of Aim 2 that allows them to retain control over their decision.

The research coordinator at each site will maintain a detailed log of all patients who were offered participation in the non-randomized observational cohort, whether they signed a consent form or not. Reasons for declining participation in the research protocol of Aim 2 will be recorded. The inclusion and exclusion criteria for Aim 2 are identical to Aim 1.

5.4 STRATEGIES FOR RECRUITMENT AND RETENTION

Patients presenting to the outpatient cardiology clinics or inpatient services of the 4 participating institutions and who are prescribed CRT device implantation or CRT-D device change-out for battery depletion will be considered for participation in this pilot randomized trial. The main investigator at each site will identify prospective patients who may require CRT device implantation. This will be achieved by screening the inpatient services and outpatient clinics of the cardiac electrophysiology services at each site. Research coordinators will verify that the prospective subjects meet all the inclusion and none of the exclusion criteria for the study. Once this information is ascertained, the investigator, research coordinator, or both will approach the patient to explain the rationale of the study and its requirements. After signing written informed consent, patients will be randomized to receive a CRT-P or a CRT-D device. Block randomization by enrolling site will be adopted. The randomization status of the patient will be communicated to the treating cardiologist. Of note, the surgical procedure for CRT-P or CRT-D implantation is similar with respect to duration and risk of the procedure, with the exception that CRT-D implantations require a larger skin incision (~1.5 inches versus 0.75 inches).

The research coordinator at each site will maintain a log of all patients who were screened for this pilot trial. The log should include reasons for why the patient did not meet either the inclusion or the exclusion criteria. Additionally, the log would also include the patient's reason for not wanting to enroll in the Aim 1 clinical trial. This log will be maintained at each individual site and redacted of identifiable information in order to send to the sponsor upon request. Use of patient initials and age will be used in place of patient's full name and date of birth.

5.5 PARTICIPANT WITHDRAWAL OR TERMINATION

During the consenting process subjects will be informed of their rights to withdraw from the study at any time without prejudice. Subjects who no longer attend their required in-office follow-up or are unable to be reached by telephone after 2 documented attempts by investigator, will be considered lost to follow-up. These subjects will not undergo any additional study activities once they have been withdrawn. The Social Security Death Index³⁷ will only be used as an adjunctive method of confirming death if no contact at all could be established with the patient or family during follow-up. Any identifiable research or medical record information recorded for, or resulting from, the subject's participation in this research study prior to the date that they formally withdraw consent may continue to be used and disclosed by the investigators for research purposes.

A patient may be discontinued from participating in this research if their device implantation procedure is not successful or is complicated by death or if they fail to follow-up after device implantation according to the research protocol requirements.

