6 STUDY PROCEDURES AND SCHEDULE

Randomization Aim

Table 1 details the baseline data collected for every enrolled patient. Baseline demographics (e.g. age, gender, and race) and clinical information (e.g. cardiac condition, comorbid conditions, echocardiographic parameters, EKG parameters) will be abstracted from the electronic medical records of each participating institution. QOL questionnaires will be obtained at enrollment and at the 6-month follow-up visit using both the RAND-36 health Status Inventory³⁵ and the Minnesota Living with Heart Failure Questionnaire³⁶. A paper and pencil option will be provided unless the patient is unable to read or write in which case the questionnaires will be administered verbally by a research coordinator.

Patients will be followed in the pilot randomized trial from the date of enrollment until study closure. During follow-up, information will be collected on procedural details and complications, as well as clinical events including death, hospitalizations, and emergency room visits. The events will be ascertained by asking the patient or their caregiver. Data pertaining to hospitalizations and emergency room visits will be readily available if they occurred at the enrolling institution. If at another institution, these data will be collected by asking the patient to sign a release of medical records form and by obtaining relevant clinical information from the other institution. The cause of death and primary reason for hospitalization will be adjudicated as cardiac (arrhythmic or non-arrhythmic) or non-cardiac by an adjudication committee that is independent from the research team. For the CRT-D arm of the study, information about appropriate and inappropriate device shocks and anti-tachycardia pacing therapies will be collected. Importantly, rates of patient screening, enrollment, randomization, and retention in the study will also be collected.

Table 1. Baseline Data	Variables Collected
Demographic variables	Age, Gender, Ethnic background, type of insurance (primary and secondary), Zip code

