9 STATISTICAL CONSIDERATIONS

9.1 STATISTICAL AND ANALYTICAL PLANS

Randomized Aim

Descriptive patient characteristics will be presented as mean (SD) for continuous variables and n (%) for categorical variables. Baseline comparisons of patients assigned to CRT-P vs. CRT-D will be performed using t-tests for continuous variables (Wilcoxon rank-sum test if non-normally distributed) and chi-squared tests for categorical variables (Fisher’s Exact Test in case of small sample sizes within cells) to confirm that the randomized treatment arms are balanced in key demographics and potential confounders. The proportion of patients experiencing major/minor procedural complications within 30 days will be reported as n (%) within each treatment arm. These complication rates will be ascertained through review of pertinent medical records following the device implantation. Mortality [as n (%)] and the 6-month QOL outcomes [as mean (SD)] within each treatment arm will be reported as well. Cost of care for the index hospitalization for CRT device implantation and for the follow-up period will be measured at the conclusion of the study and compared between the 2 cohorts using a 2-sample t-test (or Wilcoxon test if the data are non-normally distributed). Retention will be presented as n (%) completing at least 6-month of follow-up. In addition to the retention, in order to document the recruitment success, we will report the number of patients approached in order to successfully enroll n=50 patients, which will be useful information in planning a large scale trial.

Observational Aim

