All patients who do not enroll in the trial, but consent to be followed, will be enrolled in a parallel observational cohort. Patients’ clinical and demographic characteristics will be examined and compared between CRT-P and CRT-D recipients using t-tests, Wilcoxon rank-sum tests, chi-squared tests, or Fisher’s Exact tests, as appropriate. Patient satisfaction among CRT-P vs. CRT-D recipients will be assessed at baseline and 6 months after enrollment using the Satisfaction with Decision Scale. The scores will be presented as mean (SD) and tested using a 2-sample t-test (or Wilcoxon test if the data are non-normally distributed). Deceased patients will be included in the analysis (assigned the lowest possible satisfaction score of 6) to avoid survival bias in the event of differential mortality in CRT-P vs. CRT-D. Cost of care will also be presented as mean (SD) and compared between the two cohorts using a 2-sample t-test (or Wilcoxon test if the data are non-normally distributed). Multivariate modeling with adjustment for selected patient factors will be considered if there are differences in CRT-P vs. CRT-D patients on key demographics, but the power to test this difference while accounting for multiple confounders may be limited.

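### The death-index condition in section 5.5 is narrower than the definition of loss and can be read two ways, so some deaths among lost patients may go undetected

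*Combined protocol and SAP*

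**What the plan says.** Section 5.5 (Participant Withdrawal or Termination) contains three rules that bear on this point.

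- **Loss.** Patients who stop attending in-office follow-up, or who "are unable to be reached by telephone after 2 documented attempts by investigator, will be considered lost to follow-up".
- **Activity after loss.** "These subjects will not undergo any additional study activities once they have been withdrawn".
- **Death index.** It "will only be used as an adjunctive method of confirming death if no contact at all could be established with the patient or family during" (the period is follow-up).

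Section 6 gives the routine route for clinical events, including death: "The events will be ascertained by asking the patient or their caregiver". Calls fall at 30 days, 3 months, 6 months and every 6 months after that, and next of kin may also supply the information. Table 2 lists survival among the events collected through End of Study.

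Death status is then used in three places:

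- Section 9.1, Randomized Aim: "Mortality [as n (%)] and the 6-month QOL outcomes [as mean (SD)] within each treatment arm will be reported as well".
- Section 9.1, Observational Aim, for the satisfaction score: "Deceased patients will be included in the analysis (assigned the lowest possible satisfaction score of 6) to avoid survival bias".
- Section 8, where DSMB stopping turns on all-cause mortality, which that section calls the primary endpoint.

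**The concern.** The backup source for deaths is tied to a stricter condition than the one that makes a patient lost. Some patients can therefore be lost, have unknown vital status, and still not qualify for the index search. No other section requires a vital-status check on lost patients at study closure.

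Three outputs could be affected. The count of deaths by arm in Aim 1 could be too low. The all-cause mortality that the DSMB sees could be too low, or unequally low if loss differs by device. In Aim 2, a death that nobody learns of cannot receive the score of 6; it becomes a missing value, which that rule was written to prevent.

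**Working it through.** **Comparing the two rules.** Take a patient who answers the 30-day call and cannot be reached at 3 months after two documented attempts.

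- Under the loss rule the patient is lost. Earlier contact is irrelevant.
- Under the index rule, read literally, contact was established during follow-up, so the condition fails and the index is not searched.
- The mention of family works in both directions. A relative may report the death, but on the literal wording one earlier conversation with a relative also closes the index route.
- If the phrase means no contact at the time the patient became unreachable, the same patient does qualify. The text does not define it, and four sites could apply it differently.

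**The plan's own figure.** Section 9.2 uses 40 of 50 completing 6 months: 0.80 ± 1.96 × √(0.80 × 0.20 / 50) = 0.80 ± 0.111, or 68.9% to 91.1%. This reproduces. It leaves 10 non-completers. An undetected death does not change the figure, because a patient dead or lost before 6 months is a non-completer either way.

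**Illustration of size.** The documents give no mortality rate and no timing of loss, so these are assumptions: annual mortality of 10%, 15% or 20%, equal in lost and retained patients; loss at 3 months; constant hazard h = −ln(1 − annual risk).

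Mean follow-up T assumes uniform accrual over 15 months (section 9.3) of a 24-month study (Précis). Follow-up then runs from 9 to 24 months, with mean (9 + 24)/2 = 16.5. The Précis caps participation at 18 months, which gives (6 × 18 + 9 × 13.5)/15 = 15.3.

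- All deaths: D = 50 × (1 − exp(−hT/12))
- Risk of death after loss: c = 1 − exp(−h(T − 3)/12)
- Missed if all 10 are of unknown status: M1 = 10 × exp(−3h/12) × c
- Deaths by 6 months, taken as known: K = 50 × (1 − exp(−6h/12))
- Missed once those are removed from the 10: M2 = (10 − K) × c

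| T (months) | Annual mortality | D | M1 (share of D) | K | 10 − K | M2 (share of D) |
|---|---|---|---|---|---|---|
| 16.5 | 10% | 6.7 | 1.1 (16%) | 2.6 | 7.4 | 0.8 (12%) |
| 16.5 | 15% | 10.0 | 1.6 (16%) | 3.9 | 6.1 | 1.0 (10%) |
| 16.5 | 20% | 13.2 | 2.1 (16%) | 5.3 | 4.7 | 1.0 (8%) |
| 15.3 | 10% | 6.3 | 1.0 (16%) | 2.6 | 7.4 | 0.8 (12%) |
| 15.3 | 15% | 9.4 | 1.5 (16%) | 3.9 | 6.1 | 0.9 (10%) |
| 15.3 | 20% | 12.4 | 1.9 (16%) | 5.3 | 4.7 | 1.0 (8%) |

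Worked line, 15% and T = 16.5: h = 0.1625; D = 50 × 0.200 = 10.0; c = 0.167; M1 = 10 × 0.960 × 0.167 = 1.6; K = 50 × 0.078 = 3.9; M2 = 6.1 × 0.167 = 1.0.

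K treats every death by 6 months as known, including any that follow a loss at 3 months, so M2 is slightly low on that count. Withdrawals and unsuccessful implants among the 10 would reduce both M1 and M2.

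**If lost patients die at a different rate.** Assume 25% to 100% of the 10 were reached once and then lost with no informant, and 10% to 50% of those died unseen. Unseen deaths run from 10 × 0.25 × 0.10 = 0.25 to 10 × 1 × 0.50 = 5 of 50, which is 0.5 to 10 percentage points. Nothing in the documents places the trial within that range.

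**Aim 2.** If 20% of the 60 (12 patients) are lost at 3 months, deaths before the 6-month score number 12 × (1 − exp(−3h/12)) = 0.31, 0.48 and 0.65 at the three rates. That is less than one score.

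**The case against.** The strongest reply has four parts.

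**The phrase follows the definition of loss** and may simply mean that nobody could be reached at that time. On that reading there is little gap. This is a fair reading, and it rules out saying that such patients are never checked. It does not settle the matter, because the text supports either reading.

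**The index is not the only source.** Next of kin and caregivers may report a death (section 6), hospitalization and emergency-room data at the enrolling institution are available (section 6), and section 7.2 requires deaths to be reported within 48 hours of site awareness. So it cannot be said that deaths among losses are missed, only that some may be. None of these sources obliges anyone to look for a patient who has gone silent.

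**A reader might infer more than the plan states.** Section 9.1 gives no denominator or censoring rule, so the plan does not say that a lost patient is counted as alive. No figure shows that loss after an early contact is the usual pattern, or that such losses are often deaths. A flat 16% understatement is not supported either, since it requires all 10 non-completers to be of unknown status although some would be known deaths. Sections 9.1 to 9.3 describe the pilot as informing recruitment, retention, number of sites and enrollment duration; they do not say that its mortality by arm sets the pivotal event rate.

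**The stakes are limited.** Aim 1 mortality is descriptive with no test, Aim 2 plans no mortality comparison, and retention is untouched. All of this stands and limits the severity. The DSMB's use of all-cause mortality remains.

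**Conclusion.** The point holds in a limited form. The index condition is narrower than the protocol's own definition of loss and is ambiguous, so deaths among patients lost after an earlier contact may go undetected where no relative or caregiver reports them.

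Under the stated assumptions, this is about 1 to 2 missed deaths of 6 to 13 if all 10 non-completers have unknown status, and about 1 or fewer (8-12% of deaths) once known early deaths are set aside. One death in 50 is 2 percentage points. The expected effect on the Aim 2 satisfaction score is less than one patient. These sizes depend on assumed mortality, assumed timing of loss and equal mortality in lost and retained patients.

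Severity is minor to moderate: this is a feasibility pilot with descriptive mortality, but the repair is cheap.

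**What to change.** 1. In section 5.5, replace the death-index sentence with a rule such as: *At 6 months after enrollment and at study closure, vital status is sought from the Social Security Death Index and the enrolling institution's records for every Aim 1 and Aim 2 patient whose status is then unknown, whatever earlier contact was made with patient or family, except where consent to record use was withdrawn.*
2. Amend the section 5.5 sentence that ends study activities, so that it does not bar this records-only search for patients who are lost but have not withdrawn consent. Otherwise the two sentences conflict.
3. Report the number with unknown vital status in each device group beside every mortality figure, including those given to the DSMB. The DSMB meets at least quarterly, so searches at 6 months and closure serve it only in part; the count shows how incomplete the figures are in between.
4. In section 9.1, Observational Aim, apply the score of 6 to deaths found this way that occurred before the 6-month assessment.

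The cost is a brief search, at two time points, for perhaps 10 to 20 patients in sources the protocol already names, and a check that the consent form covers it. The consent pages are not in the public file, so that coverage cannot be judged here.

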5.6 PREMATURE TERMINATION OR SUSPENSION OF STUDY

This study may be temporarily suspended or prematurely terminated if there is sufficient reasonable cause. Written notification, documenting the reason for study suspension or termination, will be provided by the suspending or terminating party to each of the individual sites. It is the responsibility of each individual site to then notify their respective IRB. If the study is prematurely terminated or suspended, the PI will promptly inform the sponsors IRB and will provide the reason(s) for the termination or suspension to each site. The study may resume once concerns about safety, protocol compliance, data quality are addressed and satisfy the sponsor and IRB. Before resuming any study enrollments each individual site must first receive notification from the sponsor.

6 STUDY PROCEDURES AND SCHEDULE

Randomization Aim

Table 1 details the baseline data collected for every enrolled patient. Baseline demographics (e.g. age, gender, and race) and clinical information (e.g. cardiac condition, comorbid conditions, echocardiographic parameters, EKG parameters) will be abstracted from the electronic medical records of each participating institution. QOL questionnaires will be obtained at enrollment and at the 6-month follow-up visit using both the RAND-36 health Status Inventory³⁵ and the Minnesota Living with Heart Failure Questionnaire³⁶. A paper and pencil option will be provided unless the patient is unable to read or write in which case the questionnaires will be administered verbally by a research coordinator.

Patients will be followed in the pilot randomized trial from the date of enrollment until study closure. During follow-up, information will be collected on procedural details and complications, as well as clinical events including death, hospitalizations, and emergency room visits. The events will be ascertained by asking the patient or their caregiver. Data pertaining to hospitalizations and emergency room visits will be readily available if they occurred at the enrolling institution. If at another institution, these data will be collected by asking the patient to sign a release of medical records form and by obtaining relevant clinical information from the other institution. The cause of death and primary reason for hospitalization will be adjudicated as cardiac (arrhythmic or non-arrhythmic) or non-cardiac by an adjudication committee that is independent from the research team. For the CRT-D arm of the study, information about appropriate and inappropriate device shocks and anti-tachycardia pacing therapies will be collected. Importantly, rates of patient screening, enrollment, randomization, and retention in the study will also be collected.

Table 1. Baseline Data	Variables Collected
Demographic variables	Age, Gender, Ethnic background, type of insurance (primary and secondary), Zip code
Clinical variables	Type of heart disease (ischemic/non-ischemic), New York Heart Association class of heart failure, atrial fibrillation, BMI, tobacco and alcohol use, comorbidities that affect survival (19 conditions included in the modified Charlson comorbidity index, which include: myocardial infarction, congestive heart failure, peripheral vascular disease, cerebrovascular disease, dementia, chronic pulmonary disease, connective tissue disease, peptic ulcer disease, mild liver disease, Diabetes, hemiplegia, renal disease, end-organ damage from diabetes, any tumor, leukemia, lymphoma, metastatic solid tumor, moderate to severe liver disease, acquired immune deficiency syndrome)

Laboratory variables	Serum sodium, creatinine, calculated glomerular filtration rates, BNP
EKG variables	HR, PR, QRS, QT, QTc, Rhythm, QRS axis, QRS morphology
Medications	B-adrenergic blocking agents, Angiotensin converting enzyme inhibitors, Angiotensin receptor blockers, aldosterone, Class I and class III antiarrhythmic medications, statins, nitrates
Imaging variables	LVEF assessment with imaging modality used. Left ventricular systolic and diastolic dimensions, any other abnormality
Quality of Life	RAND-36 Health Status Inventory ³⁴ (Appendix 1) Minnesota Living with heart Failure Questionnaire ³⁵ (Appendix 2)

The milestones of data collection are detailed in Table 2. Patients enrolled in the randomized pilot trial will have baseline demographic, clinical, and pharmacological information collected after they sign written informed consent. QOL questionnaires and patient satisfaction will also be obtained at baseline. At the scheduled date of device implantation, which will be within 30 days of enrollment, procedural details will be collected including total and fluoroscopic durations of the procedure, device and lead models, and any acute major or minor procedural complications. Patients whose device implantation procedure is scheduled > 30 days from the date of enrollment have to be re-consented for participation in this trial. In follow-up, each patient will be contacted by phone at 30 days, 3 months, and 6 months post enrollment and every 6 months thereafter until the end of the study. The phone calls will be used to collect interim information from patients or next of kin regarding non-acute procedural complications or clinical events (e.g. death, hospitalization). Original medical records will be obtained for all clinical events and will be reviewed by an independent adjudication committee. Each scheduled phone visit will also be associated with a remote device interrogation to assess device function and obtain information about stored arrhythmic events.

Observational Aim

Patients enrolled in the observational cohort of Aim 2 will have demographic and clinical data collected at baseline similarly to patients enrolled in the randomized trial of Aim 1. Table 1 details the clinical variables collected at enrollment. Table 2 details the follow-up milestones. Also, patients enrolled in Aim 2 of this proposal will undergo QOL assessment using the RAND-36 Health Status Inventory³⁵ and the Minnesota Living with heart Failure Questionnaire³⁶ (Appendices 1 and 2) at baseline and at the 6-month follow-up visit which could be conducted by phone. Procedural information and complications as well as clinical events will be collected on patients enrolled in the non-randomized observational cohort, similarly to patients enrolled in Aim 1. Data on cost of care will also be collected for all patients enrolled in Aim 2.

In addition, patients enrolled in the observational cohort will be asked about their decision to receive a CRT-P or CRT-D device and will be probed for the reason (s) behind their decision and their answers will be recorded. The actual type of device implanted (CRT-P versus CRT-D) will be ascertained at the time of the implantation procedure. At baseline and at the 6-month research call, they will be assessed for their level of satisfaction with their decision about device therapy (CRT-P or CRT-D) using the Satisfaction with Decision Scale³²⁻³⁴ (Appendix 3), which assigns a score of 1 to 5 to the answer of each of 6 questions pertaining to the patient's level of satisfaction with their medical decision (lowest satisfaction score is 6 and highest is 30).

Table 2. Schedule of Events	Enrollment visit	Device implant	30-day phone call	3-month phone call	6-month visit or phone call	Every 6 months phone call	End of Study
Demographic Information	X						
Baseline Clinical Characteristics	X						
Medications	X				X	X	X
Procedural Complications		X	X				
Clinical Events (survival, hospitalizations, arrhythmias)		X	X	X	X	X	X
The Satisfaction with Decision Scale	X				X		
Quality of Life Questionnaires	X				X		
Device complications		X		X	X	X	X
Device Interrogation		X			X	X	X
Economic Data							X

